8.11.4 Vital Signs

Vital signs data will be listed by subject at each time point. Observed and change from baseline vital signs values (pulse rate, respiration rate, arterial oxygen saturation, systolic and diastolic BP, oral temperature, and weight) will be summarized by treatment at each time point period.

8.11.5 Safety Electrocardiograms

Observed values and change from baseline of 12-lead ECG parameters (HR, RR, PR, QRS, QT, QTcB and QTcF intervals) will be summarized descriptively by treatment at each scheduled time point collected. Individual ECG data will be listed. The baseline for the assessments done on Day 1 and 14 for each scheduled post-treatment timepoint will be the time-matched assessment on Day -1. The baseline for the assessments done on Day 3 to 8 will be the last assessment done before dosing on Day 1.

12-lead ECGs that the investigator flags as being abnormal (both clinically significant and not clinically significant) will be summarized separately.

In addition, the number and percentage of subjects by maximum baseline and post baseline value of QTcB and QTcF intervals, categorized as ≤ 450 msec, >450 msec and ≤ 480 msec, >480 msec and ≤ 500 msec, and >500 msec, as well as the daily maximum category, will be summarized. In addition, the same summaries (overall maximum and daily maximum) for change from baseline value of QTcB and QTcF intervals, categorized as ≤ 0 msec, >0 msec and ≤ 30 msec, >30 msec and ≤ 60 msec, and >60 msec will be tabulated based on 12-lead ECG measurements.

8.11.6 24-hour Holter Monitoring

The 24-hour Holter Monitoring data will be listed. The arrhythmias analysis by continuous Holter monitoring will be summarized. All findings will be summarized on the basis of incidence rates for the study overall (by baseline and post-baseline) and by day. A subject will be counted only once for a particular morphological abnormality if the subject experiences more than one incidence of that event.

8.11.7 Relationship Between Plasma Concentrations and Placebo-Corrected, Change from Baseline QTcF

The analyses described in this section may be conducted depending on the results observed. They will be based on the QT/QTc and PK/QTc Analysis Set.

QT/QTc Analysis Set will include all subjects in the Safety Set with measurements at baseline as well as on-treatment with at least one postdose timepoint with a valid Δ QTcF value. The QT/QTc Analysis Set will be used for the analysis of ECG parameters.

PK/QTc Analysis Set will include all subjects in both the QT/QTc and PK analysis sets with at least one pair of postdose PK and QTcF data from the same timepoint. The PK/QTc Analysis Set will be used for the exposure-response analysis.

Baseline: For all ECG parameters, baseline is defined as the measured QTc intervals from the time-matched predose timepoint on Day 1.

Exposure-Response Analysis

The relationship between NT-814 plasma concentration and Δ QTcF (change-from-baseline QTcF) will be quantified using a linear mixed-effects model with Δ QTcF as the dependent variable, NT-814 plasma concentration as a continuous covariate (zero for placebo), treatment (active or placebo) and time since drug administration as categorical factors, and a random intercept per subject. The degrees of freedom for the model estimates will be determined by the Kenward-Rogers method. From the model, the slope (i.e., the regression parameter for the concentration) and the treatment effect (defined as the difference between active and placebo) will be estimated together with 2-sided 90% CI. The estimates for the time effect will be reported with degrees of freedom and standard error (SE).

The geometric mean of the individual C_{\max} values for subjects in each of the NT-814 dose groups will be determined. The predicted effect and its 2-sided 90% CI for $\Delta\Delta$ QTcF (placebo-corrected change-from-baseline QTcF) (ie, the product with the slope estimate + treatment effect) at the geometric mean C_{\max} will be obtained for each NT-814 dose, separately. If the upper bound of the 90% confidence interval of the predicted effect at this plasma level is below 10 ms, it will be

concluded that NT-814 does not cause clinically relevant QTc prolongation. These analyses will be performed using the PK/QTc population.

The plot of the observed median-quantile NT-814 concentrations and associated mean $\Delta\Delta\text{QTcF}$ (90% CI) adjusted for diurnal effects together with the regression line presenting the predicted $\Delta\Delta\text{QTcF}$ (90% CI) (as described in the publication by Tornoe et al¹) will be used to evaluate the adequacy of the model fit to the assumption of linearity and the impact on quantifying the exposure response relationship. Additional exploratory analyses (via graphical displays and/or model fitting) will include accounting for a delayed effect (hysteresis) and the justification for the choice of pharmacodynamic model (linear versus nonlinear) as follows.

Investigation of hysteresis

If a QTc effect ($\Delta\Delta\text{QTcF}$) exceeding 10 msec cannot be excluded in the by-timepoint analysis, hysteresis, i.e., difference in peak QT response and C_{max} , will be explored through visual inspection of overlaid NT-814 concentration and $\Delta\Delta\text{QTc}$ time curves and through so called hysteresis loops for each dose of NT-814.

Appropriateness of a linear model

To assess the appropriateness of a linear model, normal QQ-plots for the residuals and plots of weighted residuals versus concentration and vs. fitted values will be produced. The scatter plot of residuals versus concentration by Loess (i.e., locally weighted scatterplot smoothing as described in the publication by Cleveland²) fitting will be also produced with an optimal smoothing parameter selected by the Akaike information criterion with a correction (AICC³). In addition, a model with a quadratic term in concentration will be fitted and the quadratic term will be tested on the two-sided 5 % level. If there is an indication that a linear model is inappropriate, additional models will be fitted, in particular:

- An E-max model;
- A log-linear model where the plasma concentration (C) is replaced by $\log(C/C_0)$, C_0 is the limit of quantification of the assay used to determine C and all values below C_0 are replaced by C_0 (i.e., $\log[C_0/C_0] = 0$).

The Exposure-Response analysis will then be repeated for the model found to best accommodate the nonlinearity detected.

By-Timepoint Analysis:

¹ Tornoe C et al. J Clin Pharmacol 2011; 7: 1035-42

² Cleveland WS. J Amer Statist Assoc 1979; 74: 829-36

³ Hurvich, CM, Simonoff, JS, and Tsai, CL 1998; J. Roy. Statist. Soc. Ser. B, 60: 271-93.

The analysis for QTcF will be based on a linear mixed-effects model with change-from-baseline QTcF (Δ QTcF) as the dependent variable, time (categorical), treatment (each NT-814 dose group and all placebo group), and time-by-treatment interaction as fixed effects, and baseline QTcF as a covariate. Baseline will be the derived QTc intervals from the ECG timepoint recorded predose on Day 1. Subjects dosed with placebo will be analyzed as a pooled group. An unstructured covariance matrix will be specified for the repeated measures at postdose timepoints for each subject. If the model with unstructured covariance matrix fails to converge, other covariance matrix such as autoregressive and compound symmetry will be considered. From this analysis, the LS mean and 2-sided 90 % CIs will be calculated for the contrast “NT-814 versus placebo” at each treatment and each postdose timepoint, separately. These analyses will be performed using the QT/QTc population.

For HR, PR, QTcB, QT, RR, and QRS intervals, the analysis will be based on the change-from-baseline post-dosing (Δ HR, Δ PR, Δ QTcB, Δ QT, Δ RR, and Δ QRS). The same model will be used as described for QTcF. The LS mean, SE and 2-sided 90% CI from the statistical modeling for both change-from-baseline and placebo-corrected change-from-baseline values will be listed in the tables and graphically displayed.

Categorical Analyses

The analyses results for categorical outliers, T-wave morphology and U-wave presence will be summarized in frequency tables with counts percentages for both number of subjects and number of timepoints. For categorical outliers, the number (percentage) of subjects as well as timepoints who had increases in absolute QTc (QTcF and QTcB) values >450, 480, and 500 msec, and changes from predose baseline of >30 or >60 msec; increase in PR from predose baseline >25% to a PR >200 msec; increase in QRS from predose baseline >25% to a QRS >120 msec; decrease in HR from predose baseline >25% to a HR <50 bpm; and increase in HR from predose baseline >25% to a HR >100 bpm will be determined. For T-wave morphology and U-wave presence, the analyses will be focused on change from baseline (i.e., treatment-emergent changes). These analyses will be performed using the QT/QTc population.

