11.2 Analysis sets

The following data sets will be used for the statistical analysis.

1. **Safety Set:** All subjects who receive at least one dose of double-blind study drug. Subjects will be analyzed according to treatment received.
2. **Pharmacokinetic (PK) Set:** all subjects who received at least one dose of active study drug and for whom the PK data are considered sufficient.
3. **Full Analysis Set (FAS):** All randomized subjects who received at least one dose of double-blind study drug and for whom the efficacy data are considered sufficient and interpretable. Subjects will be analyzed according to randomized treatment.

Analysis Sets will be identified prior to the unblinding of the study data.

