7. ANALYSIS POPULATIONS

The following data sets will be used for the analysis:

- **Safety Analysis Set:** All subjects who receive at least one dose of double-blind study drug. Subjects will be analyzed according to treatment received.
- **Pharmacokinetic Analysis Set (PKAS):** All subjects who received at least one dose of active study drug and for whom the PK data are considered sufficient. Subjects or data may be excluded from the PKAS at the discretion of the PK Scientist, including, but not limited to the following:
 - Concomitant medication which could render the plasma concentration-time profile unreliable

Any data excluded will be discussed in the CSR. Any excluded subject will have their concentration and PK parameter data listed only. Subjects who receive placebo will not be part of the PKAS.

Analysis Sets will be identified prior to the unblinding of the study data.

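### The PK/QTc Analysis Set in SAP 8.11.7 shuts out placebo subjects, but the exposure-response model run on it needs them

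*SAP*

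**What the plan says.** SAP 8.11.7 defines two populations. The QT/QTc set is drawn from the Safety Set and so contains both arms. The second is narrower: "PK/QTc Analysis Set will include all subjects in both the QT/QTc and PK analysis sets with at least one pair of postdose PK" (each PK value being matched to a QTcF value at a common timepoint). Its use is then fixed: "The PK/QTc Analysis Set will be used for the exposure-response analysis". The PK/QTc population is named again directly after the 10 ms rule.

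The term PK analysis set has to be looked up elsewhere, because SAP 8.5 lists four sets and none is a PK set. Protocol 11.2 gives "all subjects who received at least one dose of active study drug and for whom the PK data are considered sufficient". PK SAP section 7 has the same active-drug condition and adds: "Subjects who receive placebo will not be part of the PKAS".

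The model in 8.11.7 has as fixed effects "NT-814 plasma concentration as a continuous covariate (zero for placebo), treatment (active or placebo) and time since drug administration as categorical factors", plus a random intercept per subject. The slope is to be reported along with the "treatment effect (defined as the difference between active and placebo) will be estimated together with 2-sided 90% CI". The placebo-corrected prediction for each dose is the slope times geometric mean Cmax, plus that treatment effect. If the upper 90% bound is below 10 ms, it will be "concluded that NT-814 does not cause clinically relevant QTc prolongation". The section opens by making all of this conditional: "The analyses described in this section may be conducted depending on the results observed".

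**The concern.** An intersection cannot contain subjects whom one of its components excludes. If the PK set is active-only, so is the PK/QTc set, and nothing in 8.11.7 or SAP 8.5 adds placebo subjects back to it. The model written for that set then has no comparator for its treatment factor.

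This affects the one QT analysis in 8.11.7 that carries a stated conclusion, and the exploratory objective in SAP 3.2 is itself placebo-corrected. Set membership is also a rule to be settled before unblinding, and the work is divided: the SAP contents page shows a separate sign-off for 8.11.7, and the PK analysis is done by another group under the PK SAP, which bars placebo. If the conflict surfaced only when the model was run, the choice would lie between changing an analysis set late and dropping the treatment term. The second would report slope times Cmax, which is not the quantity 8.11.7 defines.

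**Working it through.** The documents give no figure for this analysis to reproduce. The question is whether the stated quantities can be estimated.

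**Inputs**
- 15 active and 5 placebo per cohort (SAP 4.1; PK SAP section 3).
- Four cohorts in PK SAP section 3 (50, 100, 150, 300 mg); up to five in the protocol.
- Ten postdose times common to the PK and ECG schedules: 0.5, 1, 1.5, 2, 2.5, 3, 4, 8, 12 and 24 h (SAP 4.9 and 4.10.5).

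**Model.** For subject i at time j:

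ΔQTcF(i,j) = β0 + β1·TRT(i) + β2·C(i,j) + γ(j) + b(i) + e(i,j)

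TRT is 1 for active and 0 for placebo, C is 0 for placebo, and γ takes 9 contrasts. The fixed-effect columns number 1 + 1 + 1 + 9 = 12. The placebo-corrected prediction at concentration c is β1 + β2·c.

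**Set as written.** Every subject has TRT = 1, so the treatment column is identical to the intercept column. Only the sum β0 + β1 is identified. Neither β1 nor β1 + β2·c can be estimated, whereas β2 can. The random subject intercept does not change this.

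**Numerical check.** Design matrices were built with illustrative concentrations. These are assumed and only fill the concentration column; the lost rank does not depend on them.

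| Cohorts | Set | Subjects | Rank / columns | Slope | Treatment effect | Prediction |
|---|---|---|---|---|---|---|
| 3 | as written | 45 | 11 / 12 | yes | no | no |
| 3 | with placebo | 60 | 12 / 12 | yes | yes | yes |
| 4 | as written | 60 | 11 / 12 | yes | no | no |
| 4 | with placebo | 80 | 12 / 12 | yes | yes | yes |
| 5 | as written | 75 | 11 / 12 | yes | no | no |
| 5 | with placebo | 100 | 12 / 12 | yes | yes | yes |

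(Yes or no: whether the quantity is estimable.)

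**Other forms in 8.11.7.** The same single rank is lost each time:
- Days 1 and 14 pooled with separate day-by-time levels: 22 of 22 with placebo, 21 of 22 without.
- The quadratic check: 13 of 13 against 12 of 13.
- The log-linear alternative: 12 of 12 against 11 of 12.

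The E-max alternative was not run, but any version that keeps an additive treatment term meets the same identity.

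**Subjects left out.** Four cohorts: 4 × 5 = 20 of 4 × 20 = 80, or 25%. Five cohorts: 25 of 100, or 25%. These are not merely a quarter of the data; they are the whole comparator.

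**The case against.** The strongest reply is that 8.11.7 makes its own meaning plain. The model assigns placebo a concentration of zero, has a placebo level in its treatment factor, and is followed by a plot of placebo-corrected QTcF. An analyst has one workable reading. A literal run would fail visibly, so no wrong estimate would be published unnoticed. On this view it is a drafting slip in a set definition.

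Other points reduce the weight further:
- The analysis is exploratory and conditional. Protocol 11.3.2 says a concentration-effect model will be built, but the protocol synopsis says only that one may be, and the stated objectives make it depend on the results. The SAP's list of tables and figures contains no concentration-QTc output.
- The by-timepoint QTcF analysis uses the QT/QTc set with pooled placebo. The hysteresis trigger also reads that analysis against 10 ms, so a placebo-corrected estimate for each dose survives.
- The express exclusion of placebo is in the PK SAP of 5 May 2017, later than the main SAP signed in March 2017, so the authors of 8.11.7 cannot have been relying on it.

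All of this stands as to size. None of it makes the definition correct. The protocol's PK set was already active-only when 8.11.7 was written, and the later PK SAP made the exclusion explicit. Clear intent in the model text does not change who belongs to the set. The requirement for paired PK data is a second obstacle for placebo subjects, because the documents do not say whether their samples are assayed.

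**Conclusion.** The point holds. The set definition contradicts the model it feeds. Followed literally, the active-minus-placebo effect, the placebo-corrected QTcF prediction with its 90% CI, and the 10 ms conclusion are not estimable; the concentration slope is. This rests on reading the PK analysis set as Protocol 11.2 or PK SAP section 7 defines it, there being no other definition in the documents. It needs no assumption about QTcF variability, concentrations or the number of cohorts.

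The impact is modest. The error would probably be noticed when the model was run, the analysis may not be run at all, and the by-timepoint and categorical QT analyses are unaffected. It should be fixed because the correction is trivial and the set is meant to be settled before unblinding.

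**What to change.** Before unblinding, redefine the PK/QTc Analysis Set in SAP 8.11.7 as those QT/QTc set subjects who meet either condition:

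- (a) they received NT-814, belong to the PK analysis set of Protocol 11.2, and have one or more postdose times with both a PK and a QTcF value; or
- (b) they received placebo, in which case their NT-814 concentration is set to zero.

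Part (b) should carry no paired-PK condition, since the model assigns these subjects a concentration rather than measuring one. This restores full rank (12 of 12), and all three quantities become estimable.

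The cost is one sentence of SAP wording. No new data are needed: placebo QTcF is already collected and already used in the by-timepoint analysis. The PK SAP can keep its active-only set for the PK analyses.

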4.10.5 Electrocardiograms

On Days 1 and 14, resting 12-lead ECG data will be collected at the following timepoints: predose and at 0.5, 1.0, 1.5, 2.0, 2.5, 3.0, 4.0, 8.0, 12.0 and 24.0 hours (all +/- 15 mins).

The same assessment schedule is also required on Day -1, starting at a time similar to that planned for Days 1 and 14. The Day -1 and Day 1, 24 hour ECGs must be performed prior to the dose of study medication the following morning (on Days 1 and 2, respectively).

Once-daily ECG recordings will be just prior to dosing (approx. 30 mins) on all other days during the inpatient stay (Days 3 to 8).

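### SAP 8.11.7 defines the QTc baseline as a time-matched Day 1 predose reading, which does not exist for 9 of the 10 postdose ECG times

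*SAP*

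**What the plan says.** SAP 8.11.7 sets one baseline for all ECG parameters: "baseline is defined as the measured QTc intervals from the time-matched predose timepoint on Day 1". Its exposure-response model regresses change from baseline in QTcF on concentration, treatment (active or placebo) and categorical time, with a random intercept per subject and no baseline covariate. The predicted effect is evaluated at each dose's geometric mean Cmax. The rule for concluding that there is no clinically relevant prolongation reads "If the upper bound of the 90% confidence interval of the predicted effect at this plasma level is below 10 ms".

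The by-timepoint analysis in the same section says "Baseline will be the derived QTc intervals from the ECG timepoint recorded predose on Day 1" and includes "baseline QTcF as a covariate". The categorical paragraph that follows refers five times to a predose baseline.

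SAP 4.10.5 schedules ECGs on Days 1 and 14 at predose and at 0.5, 1, 1.5, 2, 2.5, 3, 4, 8, 12 and 24 h. For the drug-free day it adds "The same assessment schedule is also required on Day -1, starting at a time similar to that planned for Days 1 and 14". Protocol 10.4.4 gives the same times.

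For the separate safety summaries, SAP 8.11.5 says "The baseline for the assessments done on Day 1 and 14 for each scheduled post-treatment timepoint will be the time-matched assessment on Day -1", and for the daily inpatient ECGs "The baseline for the assessments done on Day 3 to 8 will be the last assessment done before dosing on Day 1". SAP 8.1 gives a default baseline, the last value before first dosing, which yields wherever a section specifies another.

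**The concern.** A time-matched baseline needs a drug-free reading at the same clock time as each postdose reading. Day 1 before dosing cannot supply that for a profile running from 0.5 to 24 h. An analyst must drop either *time-matched* or *Day 1*, and the section-wide sentence does not say which.

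The by-timepoint sentence is clear, but it sits under its own sub-heading. The 8.1 default gives way because 8.11.7 specifies something else. The unworkable sentence is therefore the one that formally governs the exposure-response model and its 10 ms conclusion. It also bears on who enters the QT/QTc set, which requires a baseline and a valid change in QTcF. The hysteresis check is triggered by the by-timepoint result, so the two models should share a baseline. Section 8.11.7 is run only depending on the results observed, so a choice left open now could be made after data have been seen.

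**Working it through.** **Step 1: can the definition be applied?** On each profile day (SAP 4.10.5):

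| Postdose ECG times | Day 1 predose reading at the same clock time | Day -1 reading at the same clock time |
|---|---|---|
| 0.5, 1, 1.5, 2, 2.5, 3, 4, 8, 12 h (9) | none | yes |
| 24 h (1) | yes | yes |

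The Day -1 24 h ECG also falls on the Day 1 morning, since "The Day -1 and Day 1, 24 hour ECGs must be performed prior to the dose of study medication the following morning". It is at the same clock time as the predose reading, so it matches no further timepoint. The wording works for 1 of 10 times.

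**Step 2: which repair fits the text?** Deleting *time-matched* gives the single Day 1 predose value. That agrees with the by-timepoint sentence, the five predose-baseline references and the 8.1 default. Replacing Day 1 by Day -1 would also require rewriting the by-timepoint baseline sentence, the meaning of its covariate and the outlier thresholds.

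**Step 3: what does the choice do to precision?** The plan states no figure to reproduce and gives no QTc variances. Assume a between-subject SD s_b of 15 ms and a within-subject reading SD s_w of 8 ms, with no day-to-day variation at first. The part of a subject's changes that is shared across timepoints has these variances:

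- Single predose baseline: s_w² = 64, because one reading's error enters every change.
- Single predose plus baseline covariate: s_w² × s_b²/(s_b² + s_w²) = 64 × 225/289 = 49.8. The SD of this component falls by 1 − √(49.8/64) = 12%.
- Day -1 time-matched: 0, but each timepoint's own residual variance rises from 64 to 128.

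The standard error (SE) of the predicted effect at the top dose's geometric mean Cmax was computed by generalised least squares with these variances. Inputs from the documents: 15 active subjects at each of 50, 100, 150 and 300 mg and 5 placebo in each of four cohorts (PK SAP section 3), so 60 active and 20 pooled placebo; 10 paired PK/ECG times on each of Days 1 and 14. Assumed: pooling of the two days, absorption 1.2/h, half-life 12 h, and log-SD of exposure 0.413 (the sample-size value for AUC).

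| Baseline | SE (ms) | Estimate to upper 90% bound, 1.665 × SE (ms) |
|---|---|---|
| Single predose | 2.33 | 3.88 |
| Single predose + covariate | 2.13 | 3.55 |
| Day -1 time-matched | 1.07 | 1.78 |

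The covariate lowers the SE by 1 − 2.13/2.33 = 9%. It is less than 12% because postdose reading error also contributes. Over s_b 10 to 20 and s_w 6 to 10 ms the reduction is about 3% to 23%. The factor s_b²/(s_b² + s_w²) shows why: it is 400/436 = 0.92 at 20 and 6, and 100/200 = 0.50 at 10 and 10.

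Simulating the mixed model itself at SDs 15 and 8 gave SEs of 2.38, 2.17 and 1.10 ms. At a true effect of 5 ms, the chance of meeting the 10 ms rule was 0.66, 0.74 and 1.00. With an assumed day-to-day SD of 5 ms it was 0.61, 0.68 and 0.74. At a true effect of zero it was 0.97 to 1.00 throughout.

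**Step 4: is Day -1 always more precise?** No. With Day 1 data only and day-to-day SD 5, the day effect cancels from the predose change but enters the Day -1 change, with shared variance 2 × 25 = 50. At s_w = 6 the predose figure is 36. The chance of meeting the rule at a true 5 ms is then 0.84 (predose) against 0.73 (Day -1).

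**Step 5: is there bias?** Randomised placebo and the time factor remove the average diurnal course under either baseline. In a separate 40-run illustration with a true effect of about 4.9 ms, both baselines averaged 4.8 ms.

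**The case against.** The strongest reply is that this is one stray adjective. The sentence already names predose and Day 1, the by-timepoint text states the same baseline without the adjective, and nothing suggests that two versions of the change in QTcF were meant within one section. That largely stands, and it is why deletion is the natural repair. It does not make the section-wide sentence workable.

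A reader might infer that 8.11.5 and 8.11.7 contradict each other because one uses Day -1. The documents do not support this. SAP 8.1 allows a section to set its own baseline, and 8.11.5 governs separate safety summaries, so the difference may be deliberate. A reader might also take the version 2.0 note, that the ECG baseline is now the time-matched Day -1 assessment, as proof that Day -1 was meant in 8.11.7. The note names no section, 8.11.5 already carries it out for Days 1 and 14, and the SAP contents list a separate signature page, from a different organisation, for 8.11.7. It leaves some doubt about intent and shows no error in the current text.

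It is fair to call the covariate an improvement to the exposure-response model that goes beyond the wording defect. It is offered on that footing.

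**Conclusion.** The baseline sentence in 8.11.7 cannot be applied to 9 of 10 postdose times and should be corrected before unblinding, because the 10 ms conclusion rests on it. The reading consistent with the rest of the section is the single Day 1 predose QTcF.

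The consequence is for precision. At assumed SDs of 15 and 8 ms with no day-to-day variation, the distance from the estimate to the upper bound is 3.88 ms with the single predose value, 3.55 ms with the covariate and 1.78 ms with Day -1 matching. The Day -1 advantage shrinks or reverses once day-to-day variation is allowed. These sizes rest on assumed variances and an assumed PK profile, and they matter only when the true effect lies well above zero.

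It would go too far to say that the QTc result would be biased, or that counts of changes above 30 ms are compromised. The safety summaries and the 8.11.7 outlier counts each state their own baseline, so a difference between them does not follow from this defect. The analysis is exploratory and conditional.

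**What to change.** 1. Before unblinding, amend the 8.11.7 baseline sentence to one workable definition used in both the exposure-response and by-timepoint models. Deleting *time-matched* achieves this with no other edit. If the sponsor intended the Day -1 time-matched value, it should say so and change both the section-wide sentence and the by-timepoint and categorical text: baseline sentence, covariate and predose-baseline thresholds.
2. If the single predose baseline is used, add centred subject-level baseline QTcF to the exposure-response model.

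The cost is SAP wording and, for item 2, one model term; every ECG is already scheduled. With the single predose value, one reading's error enters all of a subject's changes, which the covariate partly offsets. With Day -1, any shift between that day and the treatment days enters the change, and a missing Day -1 reading loses its timepoint.

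### The concentration-QTcF model behind the 10 ms conclusion leaves out baseline QTcF, which costs precision, and fixes one slope for all women, which may make the bound too low if slopes differ

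*SAP*

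**What the plan says.** SAP 8.11.7, Exposure-Response Analysis, takes change from baseline QTcF as the outcome of a linear mixed model. The terms are NT-814 concentration (set to zero for placebo), "treatment (active or placebo) and time since drug administration as categorical factors, and a random intercept per subject". On inference it says: "The degrees of freedom for the model estimates will be determined by the Kenward-Rogers method".

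The predicted placebo-corrected effect at a dose's geometric mean Cmax is "the product with the slope estimate + treatment effect". The decision rule rests on one condition: "If the upper bound of the 90% confidence interval of the predicted effect at this plasma level is below 10 ms". When a dose meets that condition, the SAP takes it as "concluded that NT-814 does not cause clinically relevant QTc prolongation".

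The By-Timepoint Analysis in the same section has treatment, time and "time-by-treatment interaction as fixed effects, and baseline QTcF as a covariate". No reason is given for adjusting one model for baseline and not the other. The planned checks on the exposure-response model cover linearity, residual shape and hysteresis. None looks at whether the slope differs between women.

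The section opens with a condition: "The analyses described in this section may be conducted depending on the results observed".

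**The concern.** Two terms that one would expect are absent, and they act on the interval in different ways.

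- **Baseline QTcF.** The error in a woman's baseline reading is carried into all her change values. Without the covariate, that error and chance baseline differences between the active and placebo groups stay in the treatment term. Its standard error allows for this, so the cost is width and not bias.
- **Random slope.** The random intercept handles correlation from differing levels, but not from differing slopes. If women respond differently to the same concentration, the model overstates how much each woman's repeated readings tell us about the mean slope, and the slope's standard error is too small.

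The bound supports a firm statement about QTc safety. A bound that is too wide could fail to clear a drug with no relevant effect. A bound that is too low could clear a drug whose effect is at the threshold more often than the nominal 5%.

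**Working it through.** **The plan's own figures.** There are none for QTc: no variance, slope variance or precision target. The only power statement (SAP 8.12) concerns AUC ratios and has no bearing here.

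**Inputs from the documents.**
- 15 active and 5 placebo per cohort, at 50, 100, 150 and 300 mg (SAP for Pharmacokinetics, section 3): 60 active and 20 pooled placebo.
- 10 post-dose ECG times on each of Days 1 and 14 (SAP 4.10.5), each with a matching PK sample: 20 pairs per woman.
- Predicted geometric mean Cmax of 1836 ng/mL and AUC of 14040 ng.h/mL at 200 mg (protocol 9.2); log-scale SD 0.413 (SAP 8.12).

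**Assumptions.** Dose-proportional Cmax, so 1836 × 300/200 = 2754 ng/mL at 300 mg. Between-subject QTcF SD 12 to 15 ms, within-subject SD 7 to 9 ms, between-day SD 0 or 4 ms. Slope CV 0 to 100%. Placebo women included at concentration zero.

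**Step 1: baseline, in closed form.** Take one baseline reading and 20 post-dose readings, between-subject SD s, within-subject SD e, and ignore the concentration term. The group factor is 1/60 + 1/20 = 0.0667.
- Without baseline, variance of a woman's mean change = e²(1 + 1/20). SDs 15/7: 49 × 1.05 = 51.45, SE = √(51.45 × 0.0667) = 1.85 ms. SDs 12/9: 81 × 1.05 = 85.05, SE = 2.38 ms.
- With baseline, variance = s² + e²/20 − s⁴/(s² + e²). SDs 15/7: 225 + 2.45 − 184.76 = 42.69, SE = 1.69 ms. SDs 12/9: 144 + 4.05 − 92.16 = 55.89, SE = 1.93 ms.

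The simulation below gives 1.88 to 1.73 and 2.43 to 1.99 ms, in agreement. The slope's standard error barely moves (0.375 to 0.371 per 1000 ng/mL at SDs 15/7).

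With no slope variation, adding baseline cuts the mean 90% CI width at 300 mg as follows:
- SDs 15/7: 6.51 to 6.03 ms (7%)
- SDs 15/7 with day SD 4: 7.02 to 6.42 ms (9%)
- SDs 12/9: 8.41 to 7.01 ms (17%)

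**Step 2: the 10 ms rule at its boundary.** 1000 simulated trials per setting, REML, t with 78 df standing in for Kenward-Roger, true effect exactly 10 ms at 2754 ng/mL. If that effect is all slope, the mean slope is 10/2.754 = 3.63 ms per 1000 ng/mL, and CVs of 30, 50 and 100% are slope SDs of 1.09, 1.82 and 3.63. P is the chance that the upper bound falls below 10 ms (nominal 0.05).

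| SDs | Slope CV | Planned: width, coverage, P | Baseline + random slope: width, coverage, P |
|---|---|---|---|
| 15/7 | 0% | 6.51, 0.909, 0.044 | 6.09, 0.897, 0.055 |
| 15/7 | 30% | 6.60, 0.867, 0.063 | 6.42, 0.891, 0.052 |
| 15/7 | 50% | 6.76, 0.846, 0.076 | 6.92, 0.900, 0.047 |
| 15/7 | 100% | 7.38, 0.720, 0.135 | 8.49, 0.898, 0.049 |
| 15/7, day 4 | 0% | 7.02, 0.905, 0.045 | 6.45, 0.882, 0.059 |
| 15/7, day 4 | 50% | 7.22, 0.844, 0.076 | 7.20, 0.887, 0.061 |
| 12/9 | 0% | 8.41, 0.917, 0.046 | 7.09, 0.896, 0.048 |
| 12/9 | 50% | 8.60, 0.887, 0.050 | 7.87, 0.929, 0.030 |

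Monte Carlo SE of P near 0.05 is √(0.05 × 0.95/1000) = 0.007, so 0.063 alone is weak evidence; the coverage of 0.867 in that row is clearer.

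**Step 3: why.** At SDs 15/7 the planned model reports a slope SE of 0.375, 0.373, 0.380 and 0.395 at CV 0, 30, 50 and 100%. The actual sampling SD is 0.370, 0.544, 0.729 and 1.336.

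**Step 4: baseline alone is not enough.** If slopes vary and only baseline is added, P at SDs 15/7 is 0.085 at CV 50% and 0.143 at CV 100%, slightly above the planned 0.076 and 0.135. The two terms belong together.

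**The case against.** The strongest reply is that nothing in the documents shows that slopes vary. With no variation the planned interval is sound (coverage 0.909, P 0.044). That stands. A reader might infer from the missing random slope that the interval is too narrow; the documents support only that it may be.

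A reader might also take the slope's understated standard error as the size of the error in the rule. It is not. At CV 100% the slope's SD is 1.336/0.395 = 3.4 times its reported SE, but for the predicted effect, which is what the SAP tests, the ratio is 3.45/2.22 = 1.6. At CV 50% it is 2.35/2.03 = 1.2. Error rates simulated at a true effect of zero would not measure the 10 ms rule either.

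Only one interval meets the threshold, so excess width and understated slope error can offset. At SDs 12/9 and CV 50% the planned rule is at its nominal 0.050. This too stands, but it depends on the variances and does not happen at SDs 15/7.

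Omitting baseline is not a validity fault: treatment is randomised and the random intercept absorbs the shared baseline error.

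The analysis is exploratory (protocol 6.2), no primary hypothesis test is specified (protocol 11), and QTc is also assessed by timepoint, by outlier category and in the safety ECG summaries, none of which uses a common slope. This lowers the stakes. Against it, protocol 11.3.2 says a concentration-effect model will be built, and the SAP's conclusion is worded firmly.

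Kenward-Roger does not answer the slope point. It works within the covariance structure given and cannot supply a missing variance component.

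**Conclusion.** Both omissions are in the text, and the difference from the by-timepoint model is unexplained.

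Leaving out baseline QTcF biases nothing and is conservative for the 10 ms rule. It gives up about 7 to 17% of the 90% CI width at 300 mg under the assumed SDs.

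The common slope makes the bound too low only if slopes differ materially between women. At SDs 15/7 the nominal 5% becomes about 6% at CV 30%, 8% at CV 50% and 13.5% at CV 100%. It is unaffected at CV 0, and about 5% at SDs 12/9 with CV 50%.

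Confidence is high on what is missing and on the direction of each effect. The sizes rest on assumed QTc and slope variances, dose-proportional Cmax and inclusion of placebo women. The documents do not support a claim that the planned interval is in fact anti-conservative. This is a worthwhile improvement to an exploratory analysis.

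**What to change.** In SAP 8.11.7, Exposure-Response Analysis:

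1. Add baseline QTcF, centred at its mean, as a covariate. Use the same baseline that forms the change score, and say which it is, because the text that "baseline is defined as the measured QTc intervals from the time-matched predose timepoint on Day 1" is hard to read.
2. Add a random slope on concentration per subject, correlated with the random intercept (unstructured 2 × 2). If the model does not converge, drop the covariance, then the random slope, and report which fit was used.
3. Base the 10 ms conclusion on that fit.
4. State that placebo women are in the PK/QTc Analysis Set with concentration zero. The set requires PK-set membership, and the SAP for Pharmacokinetics (section 7) excludes placebo from the PK set. Read literally, the treatment effect could not be estimated, although coding placebo as zero shows that inclusion is intended.

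The cost is a few sentences and two model terms. Baseline is already collected, so item 1 is free. Item 2 risks non-convergence, and the last fallback gives no protection against slope variation. In the simulations at SDs 15/7, both changes together narrow the interval when slopes vary little (6.51 to 6.09 ms at CV 0) and widen it when they vary a lot (7.38 to 8.49 ms at CV 100%). The results were not exactly nominal everywhere: P was 0.061 with day SD 4 and CV 50%, and 0.030 at SDs 12/9 with CV 50%.
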